## STATISTICAL CONSIDERATIONS

### 10.1 Study Design/Endpoints

Primary Endpoint: Overall Response by RECIST 1.1 and iRECIST

Responses will be summarized as frequencies and percentages.

Secondary Endpoints:

- Measurement of Adverse Events by CTCAE v5.0
- Progression Free Survival (PFS) at 1 year
- Overall Survival (OS) at 1 year

After cleaning and preprocessing of the collected data, descriptive statistics will be used to summarize all adverse events. Toxicities will be aggregated as the number and percentage of patients with each type of toxicity. Kaplan Meier methods will be used to estimate overall survival and progression free survival generating median survival estimates with 95% confidence intervals (95% CIs). Multivariable survival modeling (overall survival and progression free survival) will be performed using Cox proportional hazards models and to generate Hazard Ratios (HR) and 95% CIs, with adjustment for potential patient confounders such as age, sex, smoking status, etc.

Exploratory Endpoint:

- Characterization of peripheral blood immune cell phenotypes before and after metformin, pembrolizumab and combination treatment with a particular focus on Natural Killer (NK) cells and innate immunity.
- Characterization of tumor infiltrating NK cells before and after metformin, pembrolizumab and combination treatment.
- Cytokine levels before and after metformin, pembrolizumab and combination in the plasma.
- NK effector functions before and after metformin, pembrolizumab and combination.
- Stat-3 RNA levels and phosphorylation status in NK cells and tumor tissue before and after metformin, pembrolizumab and combination treatment.
- Level of NKG2D soluble ligands before and after metformin, pembrolizumab and combination in the plasma.

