## 10.2 Sample Size/Accrual Rate

We expect that metformin and pembrolizumab combination therapy will improve ORR to 32%. Our preliminary sample size calculations indicate that 25 patients should be enough to approximately estimate the proportion of around 32% with a margin of error close to 20%. We note that ORR of pembrolizumab alone based on previous clinical studies varies between 15-20% in HNSCC; and retrospective studies show metformin increased response rates by about 10-15% in other tumor types. We also note that the calculations are based on the significance threshold of 0.05 and an 80% detection power using one-sided tests. We plan to enroll twenty-five patients total with goal of 19 evaluable (20% expected drop-out rate given dysphagia seen in head and neck cancer patients). If 6/19 achieve response, we will consider study successful and worth pursuing further in a phase II/III study. The above calculations are based on the significance threshold of 0.05 and using the critical values of the normal distribution. We expect to enroll the patients over 18-24 months.

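### The primary ORR has no planned confidence interval, and the 6/19 success rule does not have the 0.05 error and 80% power that Section 10.2 states

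*Combined protocol and SAP*

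**What the plan says.** Section 10.2 (Sample Size/Accrual Rate) is built on precision. It expects an ORR of 32% with the combination and holds that "25 patients should be enough to approximately estimate the proportion of around 32% with a margin of error close to 20" per cent. As context it notes that "ORR of pembrolizumab alone based on previous clinical studies varies between 15-20% in HNSCC". It then states that "the calculations are based on the significance threshold of 0.05 and an 80% detection power using one-sided tests". It plans 25 enrolled and 19 evaluable patients, and sets a decision rule: "If 6/19 achieve response, we will consider study successful". The paragraph ends: "The above calculations are based on the significance threshold of 0.05 and using the critical values of the normal distribution".

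Section 10.1 (Study Design/Endpoints) gives the whole analysis of the primary endpoint in one sentence: "Responses will be summarized as frequencies and percentages". The same section plans 95% confidence intervals for median PFS and OS and for the hazard ratios. Neither section, nor Section 13 on measurement of effect, names an interval or a test for the ORR.

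**The concern.** There are two gaps.

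First, the trial is sized so that one proportion is estimated with a given precision, yet no measure of precision is planned for that proportion. The secondary survival endpoints get intervals and the primary endpoint does not. If the method is left open, it can be chosen after the count is known. With 19 patients that choice can decide whether a reference rate is excluded.

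Second, Section 10.2 attaches a significance threshold, a power and a one-sided test to calculations that are a margin of error plus a fixed cut-off. Power does not enter a margin-of-error calculation. A reader will take 0.05 and 80% as properties of the 6/19 rule, because that rule is the only decision in the section. If the rule lacks those properties, the case for going on to a phase II/III study would rest on weaker evidence than the plan claims.

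**Working it through.** **Inputs (all from Section 10.2).** Expected ORR 0.32; reference 0.15 to 0.20; 25 enrolled; 19 evaluable; success at 6/19, read as 6 or more. I use 19 because the success rule does. (19/25 = 76%, a loss of 24%, whereas 25 × 0.80 = 20.)

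**1. The plan's own figure.** Normal half-width = z × √(p(1−p)/n), with p = 0.32.
- Two-sided 0.05, n = 25: 1.96 × √(0.32 × 0.68/25) = 18.3 points. This fits a margin close to 20.
- Two-sided 0.05, n = 19: 1.96 × √(0.32 × 0.68/19) = 21.0 points.
- One-sided z = 1.645: 15.4 points at 25 and 17.6 at 19.

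The margin therefore reproduces with a two-sided normal value, not with the one-sided test that the section names.

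**2. Error rate and power of the rule.** P(X ≥ 6) = 1 − Σ C(19,x) pˣ(1−p)¹⁹⁻ˣ for x = 0 to 5. At p = 0.15 the six terms are 0.0456, 0.1529, 0.2428, 0.2428, 0.1714 and 0.0907. They sum to 0.9463, which leaves 0.0537.

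| True ORR | P(6 or more of 19) | Meaning |
|---|---|---|
| 15% | 5.4% | false-positive rate, low end of reference |
| 18% | 11.1% | false-positive rate, within reference |
| 20% | 16.3% | false-positive rate, high end of reference |
| 32% | 60.1% | power at the design value |

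**3. Would another cut-off at 19 do?** Requiring 7 or more lowers the error at 15% to 1.6% (0.0537 − C(19,6) × 0.15⁶ × 0.85¹³ = 0.0537 − 0.0374). Power at 32% is already only 60.1% with a cut-off of 6, and a higher cut-off can only reduce it. So no cut-off at 19 gives both 0.05 and 80%, even against 15%. As a rough guide, the one-sample normal formula n = [(1.645√(p₀(1−p₀)) + 0.842√(0.32 × 0.68))/(0.32 − p₀)]² gives 34 patients for p₀ = 0.15 and 77 for p₀ = 0.20.

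**4. What a result at the threshold would show.** 95% intervals for an observed 6/19 = 31.6%:

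| Method | Lower | Upper | Width (points) |
|---|---|---|---|
| Normal (Wald) | 10.7% | 52.5% | 41.8 |
| Clopper-Pearson | 12.6% | 56.6% | 44.0 |
| Wilson | 15.4% | 54.0% | 38.6 |

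Only Wilson excludes 15%, and none excludes 20%. The exact one-sided 95% lower bound is 14.7%, which agrees with the 5.4% in step 2. At 8/19 the lower limits are 19.9% (normal), 20.3% (Clopper-Pearson) and 23.1% (Wilson), so there the choice of method decides whether 20% is excluded.

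**The case against.** The strongest reply is that Section 10.2 calls its calculations preliminary and approximate, that the margin is tied to 25 patients, where it does reproduce, and that no null rate is formally stated, so 0.05 and 80% were never promised for the 6/19 rule. Part of this stands: the margin statement is sound for 25 patients, and 21.0 points at 19 is not far off. But the section's last sentence applies the 0.05 threshold to everything above it, and the success rule comes immediately before. If the rule was not meant to carry these properties, the plan gives it none, and the same correction is needed.

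A reader might go further and infer that the trial's error bars for ORR will be too narrow or impossible, or that a normal interval would overstate activity. The documents do not support this.
- No section plans a normal interval for analysis; the normal critical values describe the sizing. An interval that is not planned cannot be too narrow.
- If one were used at 19 patients, its coverage would be 95.1% at a true ORR of 32%. It would be 93.8% at 15%, 86.8% at 18% and 91.0% at 20%. The shortfall at 18-20% comes mainly from upper limits that are too low (11.9% and 8.3% of the time), which understates activity.
- At 6/19 its lower limit (10.7%) is the most cautious of the three methods.
- A negative lower limit needs 1 to 3 responses, and zero width needs none. All of these are far from the success threshold.

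**Conclusion.** The concern holds as a reporting gap together with a misstated operating characteristic. The primary endpoint of a trial sized on precision has no planned interval. The 6/19 rule has a false-positive rate of 5.4% to 16.3% across the plan's own reference range and 60.1% power at its own expected rate, against the stated 0.05 and 80%. The power shortfall of about 20 points is the larger departure; the error rate is close to 0.05 only at the lowest reference value. A success at exactly 6/19 does not exclude the 15-20% reference by the exact interval.

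This rests on four assumptions: 19 patients are evaluable, success means 6 or more, the comparison rate lies between 15% and 20%, and responses are independent with a common probability. The finding does not show that a trial of this size is unsuitable as a signal-finding study; it shows that the strength of the signal is misdescribed.

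**What to change.** **Section 10.1.** Add that the ORR will be reported with a two-sided 95% Clopper-Pearson interval, using the evaluable patients as denominator. The method should be named in advance, because at 6/19 the choice decides whether 15% is excluded. Wilson is a defensible alternative, but its lower limits at 6/19 and 8/19 are higher than the exact ones, so it should not be left as an option to be settled later.

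**Section 10.2.** Restate precision at 19 evaluable patients from the exact interval (12.6% to 56.6% at 6/19). Give the rule's exact properties: 5.4% at a true ORR of 15%, 16.3% at 20% and 60.1% at 32%. Let these replace the 0.05, 80% and one-sided statements, and say that a result at the threshold does not by itself exclude the reference range.

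**Cost.** A sentence in 10.1 and a few in 10.2, with no change to enrolment, visits or data. The stated figures become less favourable, and at 6/19 the interval is 44.0 − 41.8 = 2.2 points wider than the normal one. If the sponsor wishes to keep 0.05 and 80%, more patients would be needed, and the reference rate would have to be fixed first.

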## PLANNED ENROLLMENT REPORT

Racial Categories	Ethnic Categories				Total
	Not Hispanic or Latino		Hispanic or Latino		
	Female	Male	Female	Male	
American Indian/ Alaska Native	0	0	0	0	0
Asian	0	0	0	0	0
Native Hawaiian or Other Pacific Islander	0	0	0	0	0
Black or African American	1	2	0	0	3
White	7	13	0	0	15
More Than One Race	1	1	0	0	2
Total	9	16	0	0	25

PHS 398 / PHS 2590 (Rev. 08/12 Approved Through 8/31/2015)

OMB No. 0925-0001/0002

### 10.3 Early Stopping Rules:

In order to verify safety of the combination of metformin and pembrolizumab, an early stopping rule will be used if 3 out of 9 (33%) of the safety lead-in develop DLTs (see definition above). The lead-in will be on a rolling basis but if three patients develop DLTs, the study will be stopped so that safety may be investigated by the DSMB. If DLTs are confirmed, the study will be closed to enrollment due to safety concerns.

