peripheral NK cells as well as increased activation and expression of the activating receptor, NKG2D. In addition, NK cells express PD-1 and therefore, can potentially be inhibited by its ligands suggesting treatment with PD-1 inhibitors could lead to subsequent activation of not only cytotoxic T cells but also NK cells. Therefore, combining metformin and PD-1 inhibition may enhance NK cell function and tumor cytotoxic response leading to improved survival outcomes. In fact, Scharping et al. showed that combining PD-1 blockade and metformin did enhance tumor growth inhibition in a melanoma mouse model which was thought to be due to a metformin related decrease in hypoxia allowing for immune cell infiltration. In this study, we will combine metformin and pembrolizumab in a phase II clinical trial in order to test clinical overall response in recurrent and/or metastatic HNSCC patients as well as determine the importance of NK cell infiltration, activation and possible mechanism in which the combination therapy exerts this effect.

Pembrolizumab and metformin have documented safety in several previous clinical trials and retrospective studies. A retrospective study comparing metastatic melanoma patients receiving PD-1 inhibitors versus those that were on the combination with metformin not only showed a trend towards improved clinical response, but also similar safety profiles with 60.6% vs. 59% immune related side effects respectively. A phase IB study in NSCLC also demonstrated early efficacy signals for the combination and similar safety profiles between pembrolizumab alone and combination. However, it is important to note that patients on these studies received metformin at doses of 500-1000mg daily. Given documented safety of the combination but not at the higher dose of metformin of 2000mg daily, we therefore feel it is reasonable to proceed with a phase II study with safety lead-in to determine dose limiting toxicity (DLTs) in this group of patients.

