## 7.7 Definition of Dose-Limiting Toxicity

### 7.7.1 Lead-in Safety Analysis

The first nine patients will be enrolled as the lead-in population. Safety analysis will be performed with this population and will be analyzed on a rolling basis. Monthly review with all active sites will be held to determine if any of these first 9 patients have experienced a dose limiting toxicity, DLT, (described below) to evaluate the safety of the combination. Safety analysis will be considered complete after the ninth patient has completed 28 days of combination treatment. Patients will continue to be enrolled past the initial safety cohort, but if at any time, safety analysis reveals >3 out of the 9 patients in the safety cohort have developed a DLT, then no further patients may be enrolled due to excess toxicity with this combination.

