### 7.7.2 Dose Limiting Toxicity

Dose limiting toxicity (DLT) is defined as the appearance of side effects during treatment that are attributed to treatment and severe enough to prevent continuation of treatment or grade 3 or 4 non-hematologic toxicities other than alopecia, nausea or vomiting and that in the case of pembrolizumab, do not resolve with steroids after four weeks. If more than three of nine patients develop a DLT, then combination will be considered unsafe and the study will not proceed. Patients are assessed for DLTs during the lead-in period as well as for the first 28 days of combination treatment.

Management and dose modifications associated with the above adverse events are outlined in Section 8.

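### At exactly three confirmed DLTs in the nine-patient lead-in, section 10.3 closes enrolment while sections 7.7.1 and 7.7.2 leave it open

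*Combined protocol and SAP*

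**What the plan says.** Section 10.3 (Early Stopping Rules) sets the trigger at three: "an early stopping rule will be used if 3 out of 9 (33%) of the safety lead-in develop DLTs". It repeats the number in words, stops the study at that point so that the DSMB can investigate, and then states the consequence: "If DLTs are confirmed, the study will be closed to enrollment due to safety concerns".

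Section 7.7.1 (Lead-in Safety Analysis) sets a different trigger. Further enrolment is barred if "safety analysis reveals >3 out of the 9 patients in the safety cohort have developed a DLT". Short of that, "Patients will continue to be enrolled past the initial safety cohort". Oversight there is a monthly review with the active sites; neither a pause nor a DSMB step is mentioned.

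Section 7.7.2 (Dose Limiting Toxicity) agrees with 7.7.1: "If more than three of nine patients develop a DLT, then combination will be considered unsafe and the study will not proceed".

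On who is counted, section 7.7.1 says "The first nine patients will be enrolled as the lead-in population" and "Safety analysis will be considered complete after the ninth patient has completed 28 days of combination treatment". No replacement rule is given. Section 7.7.2 runs the DLT window through the single-agent lead-in and the first 28 days of combination. Section 13.1.1 counts every patient as evaluable for toxicity from the first dose of either drug.

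**The concern.** The conflict lies exactly on the decision boundary. If three of the nine have confirmed DLTs, a site or DSMB member working from section 10 would close the study to enrolment, and one working from section 7 would go on enrolling. Enrolment is rolling, so the difference decides whether further patients are exposed.

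The lead-in exists because of a gap in the safety record that section 3.3 acknowledges: "Given documented safety of the combination but not at the higher dose of metformin of 2000mg daily". A rule meant to fill that gap should give one answer for each possible count, and this one does not for a count that is among the likelier ones if the combination is toxic.

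A lesser point is the denominator. A patient who leaves before any combination treatment says little about the combination but, as written, may still occupy one of the nine places. The Summary of Protocol Changes (item 5) says accrual was raised because more Arm 2 patients than expected withdrew before starting metformin or before reaching steady state. It gives no rate and does not say whether any of them were among the first nine.

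**Working it through.** **The stated percentage.** 3/9 = 33.3%, which matches the 33% printed in section 10.3. Four of nine would be 44.4%. So the three in section 10.3 is not a slip for more than three. Likewise, 7.7.1 uses the symbol and 7.7.2 spells it out in words, so that version is not an obvious slip either.

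**The rules side by side, by number of lead-in patients with a confirmed DLT.**

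| DLTs in nine | Section 10.3 | Sections 7.7.1 and 7.7.2 |
|---|---|---|
| 0 to 2 | continue | continue |
| 3 | stop for DSMB review, then close enrolment | closing threshold not met; enrolment goes on |
| 4 or more | stop for DSMB review, then close enrolment | close enrolment; combination unsafe |

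The only row that differs is three. Reading the text as a two-step rule, pause at three and close at four, does not remove the difference: section 10.3 closes after three confirmed DLTs and asks for no fourth.

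**How often the differing row would occur.** Inputs: n = 9 (section 7.7.1), thresholds 3 (section 10.3) and 4 (sections 7.7.1 and 7.7.2). The true DLT rate p is not in the documents and is assumed. Let X be the number of DLTs, X ~ Binomial(9, p), with all nine evaluable.

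- P(X = k) = C(9, k) p^k (1 − p)^(9 − k)
- P(X ≥ 3) = 1 − P(0) − P(1) − P(2)
- P(X ≥ 4) = P(X ≥ 3) − P(3)

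Worked for p = 0.30: P(0) = 0.7^9 = 0.0404; P(1) = 9 × 0.3 × 0.7^8 = 0.1556; P(2) = 36 × 0.09 × 0.7^7 = 0.2668. Hence P(X ≥ 3) = 1 − 0.4628 = 0.5372. P(3) = 84 × 0.027 × 0.7^6 = 0.2668, so P(X ≥ 4) = 0.5372 − 0.2668 = 0.270 to three decimals.

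| Assumed true DLT rate | P(X ≥ 3) | P(X ≥ 4) | P(X = 3) | Ratio of the first two |
|---|---|---|---|---|
| 10% | 5.3% | 0.8% | 4.5% | 6.4 |
| 15% | 14.1% | 3.4% | 10.7% | 4.2 |
| 20% | 26.2% | 8.6% | 17.6% | 3.1 |
| 30% | 53.7% | 27.0% | 26.7% | 2.0 |
| 33% | 61.5% | 34.2% | 27.3% | 1.8 |
| 40% | 76.8% | 51.7% | 25.1% | 1.5 |
| 50% | 91.0% | 74.6% | 16.4% | 1.2 |

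P(X ≥ 3) is the chance that section 10.3 halts the study for DSMB review. P(X ≥ 4) is the chance that sections 7.7.1 and 7.7.2 close it. The difference, P(X = 3), is the chance of reaching the count at which the sections part.

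**The case against.** The best reply is that sections 7.7.1 and 7.7.2 give a sufficient condition for closing and do not forbid closing earlier. The sentence about continuing enrolment can be read as saying only that accrual is not held while the nine are observed. On that reading, a site that obeys section 10.3 at three DLTs breaches nothing in section 7.7. This has some force: the sections do not give flatly opposite commands. But a reader of section 7.7 alone would keep enrolling at three, and section 7.7.2 reserves the label of unsafe for more than three. The inconsistency stands.

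Second, oversight softens the risk. Section 10.3 brings in the DSMB, section 7.7.1 has monthly site review, and section 14.3.1 provides an independent board. That makes the conflict more likely to be noticed. It does not settle it, since the board is advisory and would face two rules.

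Third, closure under section 10.3 needs confirmation, whose probability is unknown. As a measure of different closure decisions, P(X = 3) is therefore an upper bound. As a measure of different handling it is fair, because section 10.3 already halts the study at three, before confirmation.

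Fourth, the choice of three over four is a judgement. No acceptable DLT rate is stated, and two of the three sections say more than three. This is right: the error is having two rules, and the recommendation between them is a preference for the more cautious one.

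Fifth, the lead-in may already be complete, since this is the sixth amendment. The documents do not say. If it is, the conflict matters in practice only if the count was exactly three.

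On the denominator, section 5.2 allows registration to be cancelled when no protocol therapy is given, which partly covers the earliest withdrawals. It does not cover an Arm 2 patient who had pembrolizumab but never metformin. This remains a point to clarify, not a demonstrated error.

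**Conclusion.** The concern holds and should be corrected. Section 10.3 closes enrolment after three confirmed DLTs in nine; sections 7.7.1 and 7.7.2 close it only after four. All three are current text, each version is internally consistent, and I found no statement of precedence. The schema and some front matter were not in the text I had, so I cannot exclude one there.

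The contradiction itself rests on no assumption. Its size does: with nine evaluable patients and an assumed DLT rate of 20% to 50%, the chance of landing on the disputed count is 16 to 27 percentage points. At 30% the choice of section doubles the chance of a stop. The primary endpoint and its analysis are not affected; this is a safety decision rule.

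**What to change.** Put one threshold and one consequence, in identical words, in sections 7.7.1, 7.7.2 and 10.3. I recommend the rule already in 10.3: pause at three DLTs for DSMB review, and close enrolment if they are confirmed.

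At the same time, define a DLT-evaluable patient as one who has had a DLT or has completed 28 days of combination. Replace non-evaluable lead-in patients with the next planned enrollees until nine are evaluable.

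If the lead-in is already complete, report the number of DLTs and of evaluable patients to the DSMB. If the number of DLTs was exactly three, record the board's decision on which rule applied.

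The cost is wording in three sections. No patients are added, because replacements come from the planned 25, though declaring the lead-in complete may take slightly longer. The stricter threshold also pauses a tolerable combination more often: 5% rather than 1% at a true DLT rate of 10%, and 14% rather than 3% at 15%. If the sponsor regards 20% as tolerable, the figures are 26% and 9%. If the sponsor prefers four for that reason, it should say so and change section 10.3 to match.
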